### 10.6. Drug Accountability

The Investigator or designee is responsible for taking an inventory of each shipment of ANK-700 received and comparing it with the accompanying drug order form. All unused ANK-700 will be retained at the site. After full drug accountability and reconciliation, the Investigator will either dispose of any unused ANK-700 at the clinical study site per site procedures or return unused ANK-700 to the Sponsor or its designee. Disposition of all ANK-700 should be documented, including any ANK-700 that is lost or damaged.

Study ANK-700-01 in Relapsing-Remitting Multiple Sclerosis

### **10.7.** ASSIGNMENT TO TREATMENT

Once a patient has met all entry criteria, he or she will be assigned a distinct patient identifier. If a patient discontinues from the study, the patient identifier will not be reused, and the patient will not be allowed to reenter the study.

In Part A, patients will be assigned to receive open-label ANK-700 at a dose level based on the next available spot in the cohort(s) currently being enrolled. Patients in Part A may be replaced if they do not receive the full dose of study drug or do not complete the D15 visit, as long as the discontinuation was not due to a DLT

In Part B, patients will be stratified based upon their use of fumarate at study entry within the IRT system. For the sentinel group, the first 2 eligible patients within each cohort will be randomized through IRT in a 1:1 ratio to receive either ANK-700 or PBO. After completion of the sentinel dosing in each cohort, the remaining 10 patients will be randomized to ensure an overall 2:1 randomization to ANK-700 and PBO. Patients in Part B may be replaced if they do not receive the full 3 doses of study drug or do not complete the D22 visit, as long as the discontinuation was not due to a DLT.

# 11. SAFETY DATA COLLECTION, RECORDING, AND REPORTING

### 11.1. ADVERSE EVENTS

### 11.1.1. Definition of an Adverse Event

An AE is defined as any untoward medical occurrence associated with the use of a drug, or with study participation, whether or not consider related to study treatment.

An AE can therefore be any unfavorable and unintended sign (e.g., an abnormal laboratory finding), symptom, or disease temporally associated with the use of the medicinal product, whether or not considered related to the medicinal product.

AEs include worsening of a pre-existing medical condition, including MS, as well as CS changes from baseline laboratory values/conditions. Worsening of the preexisting medical condition (e.g., diabetes, hypertension) means that it has increased in severity, frequency, and/or duration, and/or has an association with a significantly worse outcome. A pre-existing condition that has not worsened during the study is not considered an AE.

# 11.1.2. Protocol-Defined MS Relapse

Patients who present with suspected clinical relapse should be assessed by EDSS and/or MRI (with and without contrast and may include spinal cord), as appropriate. Protocol-defined MS relapse for this study is:

• Sudden episode of new symptoms or worsening existing MS symptoms that lasts for ≥ 24 hours and occurs ≥ 30 days after conclusion of previous relapse (patient must be stable or improving for the 30 days immediately preceding relapse) and for which there is no other cause such as infection or environmental triggers. Episodic spasms, sexual dysfunction, fatigue, mood change, or bladder or bowel urgency or incontinence will not suffice to establish the diagnosis of a relapse.

### 11.1.3. Definition of a Serious Adverse Event

An SAE is any untoward medical occurrence that at any dose:

- results in death
- is immediately life-threatening
- requires inpatient hospitalization or prolongation of existing hospitalization
  - Elective or pre-planned treatment for a pre-existing condition that is unrelated to the indication under study and has not worsened since signing the ICF (documented as medical history on the eCRF) is not considered an SAE.
  - Scheduled therapy for the target disease of the study, including admissions for transfusion support or convenience, is not considered an SAE.
- results in persistent or significant disability/incapacity

Study ANK-700-01 in Relapsing-Remitting Multiple Sclerosis

- results in congenital anomaly/birth defect
- is considered an important medical event
  - If an AE does not meet 1 of the serious criteria, but the Investigator or Sponsor considers an event to be clinically important, the event could be classified as an SAE under the criterion of an "Important Medical Event." Examples of such medical events may include allergic bronchospasm requiring intensive treatment in an emergency room or at home, or blood dyscrasias or convulsions that do not result in inpatient hospitalization.

### 11.2. PROCEDURES FOR RECORDING AND REPORTING ADVERSE EVENTS

# 11.2.1. Recording Adverse Events

Patients will be instructed to report all AEs and will be asked a general health status question at each study visit. All AEs and SAEs occurring in patients will be recorded in the eCRF from the time of signing the ICF through the Final Study Visit/phone call. An AE will be followed until it is resolved, has returned to baseline, or is determined to be a stable or chronic condition.

At each protocol-required visit (including safety follow-up phone call) during the study, all AEs that have occurred since the previous visit must be reviewed by the Investigator. The Investigator must determine if the AE is serious or nonserious.

The Investigator must assign the following AE attributes:

- AE diagnosis or syndrome(s) if known
  - If not known at time of the report, record the signs and/or symptoms as AEs and provide an updated report with diagnosis when obtained
- dates of onset and resolution
- severity as defined per protocol
- assessment of relatedness to ANK-700/PBO
- action taken with each ANK-700/PBO dose because of the AE

In general, an AE that is the primary cause of subsequent events should be identified by the primary cause (e.g., for dehydration because of diarrhea, the AE would be diarrhea). However, AEs occurring secondary to an initiating event that are separated in time should be recorded as independent events (e.g., for sepsis secondary to pneumonia, both events should be recorded).

Confirmed and suspected SARS-CoV-2 infections and/or COVID-19 cases will be recorded in the AE eCRF.

# 11.2.2. Relationship to ANK-700

The Investigator must assess whether the AE may be related to ANK-700 (study drug) or any protocol mandated procedure, when applicable. The relationship is defined below:

Relationship assessments that indicate the event is "Not Drug Related":

Study ANK-700-01 in Relapsing-Remitting Multiple Sclerosis

• None: The event is related to an etiology other than the study product administration (the alternative etiology must be documented in the study patient's medical record).

• Remote: The event is unlikely to be related to the study product and likely to be related to factors other than study product.

Relationship assessments that indicate the event is "Drug Related":

- Possible: There is an association between the event and the administration of ANK-700, and there is a plausible mechanism for the event to be related to the study product; but there may also be alternative etiology, such as characteristics of the patient's clinical status or underlying disease.
- Probable: There is an association between the event and the administration of ANK-700, there is a plausible mechanism for the event to be related to ANK-700, and the event could not be reasonably explained by known characteristics of the patient's clinical status or an alternative etiology is not apparent.
- Definite: There is an association between the event and the administration of ANK-700, there is a plausible mechanism for the event to be related to the ANK-700, and causes other than ANK-700 have been ruled out and/or the event re-appeared on re-exposure to ANK-700.

# 11.2.3. Adverse Event Severity

The Investigator will assess the Grade of the AE per the NCI-CTCAE v5.0 or higher (Appendix 1). Toxicities that are not specified in the NCI-CTCAE will be defined as follows:

- Grade 1: Mild; asymptomatic or mild symptoms; clinical or diagnostic observations only; intervention not indicated
- Grade 2: Moderate; minimal, local, or noninvasive intervention indicated; limiting age-appropriate instrumental activities of daily living (ADL)
- Grade 3: Severe or medically significant but not immediately life-threatening; hospitalization or prolongation of hospitalization indicated; disabling; limiting self-care ADL
- Grade 4: Life-threatening consequences; urgent intervention indicated
- Grade 5: Death related to AE

Note: It is important to distinguish between SAEs and severe AEs. Severity is a measure of intensity, whereas seriousness is classified by the criteria based on the regulatory definitions as described in Section 11.1.3.

# 11.2.4. Abnormal Laboratory Values

The Investigator is responsible for reviewing clinical laboratory tests determining whether an abnormal value represents a CS change from the patient's baseline value. In general, abnormal laboratory findings without clinical significance (based on the Investigator's judgment) should

Study ANK-700-01 in Relapsing-Remitting Multiple Sclerosis

not be recorded as AEs. In general, an abnormal laboratory test result should be reported as an AE if the laboratory result:

- requires an adjustment or discontinuation of ank-700
- requires treatment with or adjustment to concomitant medications
- is considered to be an AE by the Investigator

## 11.2.5. Medication Errors, Misuse, and Abuse of ANK-700

Overdose, medication error, off-label use, misuse, abuse, and occupational exposure are defined as follows:

- Overdose: refers to the administration of a quantity of ANK-700 given per administration or cumulative that is above the maximum dose according to the protocol
- Medication error: refers to an unintentional error in dispensing or administration of ANK-700 not in accordance with the protocol
- Off-label use: relates to situations where ANK-700 is intentionally used for medical purpose not in accordance with the protocol
- Misuse: refers to situations where ANK-700 is intentionally and inappropriately not used in accordance with the protocol
- Abuse: corresponds to the persistent or sporadic, intentional excessive use of ANK-700, which is accompanied by harmful physical or psychological effects
- Occupational exposure: refers to exposure to ANK-700 because of one's professional or nonprofessional occupation

Overdoses, medication errors, abuse, or misuse will be collected as part of investigational medicinal product dosing information and/or as a protocol violation, as required.

# 11.2.6. Reporting of Serious Adverse Events

SAEs will be recorded on the appropriate eCRF and reported to the Sponsor within 24 hours of the Investigator's first knowledge of the event, even if the experience does not appear to be related to ANK-700, from the time of signing ICF through the final Follow-Up Visit/phone call.

The initial SAE eCRF must be as complete as possible and include details of the current illness and SAE as well as an assessment of the relationship between the event and ANK-700. Additional information relating to a previously reported SAE must also be reported within 24 hours of the Investigator's first knowledge of information. The Investigator may also be asked, by the Sponsor or designee, to provide clarifications or additional information.

If the Investigator becomes aware of an SAE considered related to ANK-700 occurring more than 30 days after the last dose of ANK-700, the SAE must be reported as described above.

Anokion US, Inc.

# 11.2.7. Reporting of Serious Adverse Events to Regulatory Authorities, Ethics Committee, and Institutional Review Board

The Sponsor or designee will determine expectedness of the Sponsor's product for each reported SAE based on the appropriate reference safety information per local country requirements. The Sponsor or designee shall notify regulatory authorities of serious, unexpected, and related AEs or other AEs, per local requirements.

The Sponsor or designee shall notify the Investigator of serious, related, and unexpected AE(s) submitted to the regulatory agencies, per local country requirements.

The Investigator will notify the appropriate Institutional Review Board (IRB)/Local Ethics Committees (LECs) of serious, related, and unexpected AE(s), or significant risks to patients, per local country requirements. The Investigator must keep copies of all AE information on file, including correspondence with the Sponsor or IRBs/LECs.

# 11.2.8. Pregnancy and In Utero Drug Exposure

ANK-700 has not been evaluated in pregnant or nursing women. Thus, pregnant women or WCBP who are not using effective contraception are excluded from this study (see Section 8 and Section 6.1.9 for instructions on birth control and pregnancy testing, respectively).

Pregnancies occurring in patients or partners of male patients are considered immediately reportable events if the pregnancy occurs during the study treatment through the Safety Follow-Up Visit (D15 in Part A; D22 in Part B) after the patient's last dose of ANK-700. If a pregnancy occurs in a patient, ANK-700 must be discontinued immediately. The pregnant woman should be referred to an obstetrician/gynecologist experienced in reproductive toxicity for further evaluation and counseling.

The pregnancy must be reported to the Sponsor or designee within 24 hours of the Investigator's knowledge of the pregnancy by recording it on the appropriate eCRF.

The Investigator will follow the pregnancy (the patient or the patient's partner) until completion of the pregnancy and must notify the Sponsor of the pregnancy outcome within 24 hours of the Investigator's knowledge of the outcome. The Investigator will provide this information by recording it on the appropriate eCRF. This notification includes pregnancies resulting in live, "normal" births.

If the pregnant patient/patient's pregnant partner experiences an SAE during pregnancy, or the outcome of the pregnancy meets any of the serious criteria (i.e., spontaneous abortion [any congenital anomaly detected in an aborted fetus is to be documented], stillbirth, neonatal death, or congenital anomaly), the Investigator should follow the procedures for reporting SAEs (i.e., report the event to the Sponsor or designee within 24 hours of the Investigator's knowledge of the event).

All neonatal deaths and congenital anomalies that occur within 30 days of birth (regardless of causality) should be reported as SAEs to the Sponsor or designee. In addition, any infant death or

Study ANK-700-01 in Relapsing-Remitting Multiple Sclerosis

congenital anomaly occurring after 30 days that the Investigator suspects is related to the in utero exposure to ANK-700 should also be reported to the Sponsor or designee.

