#### 4.7. Dose Escalation Safety Monitoring Period

In Part A, the dose-escalation safety monitoring period is from the beginning of the IV administration of ANK-700 through the D15 clinic visit. Any AEs that meet the criteria defined in Section 4.6 but occur after the dose-escalation safety monitoring period of Part A, may be considered by the SMC in the evaluation for Part B dose selection.

The dose-escalation safety monitoring period in Part B is from the beginning of the first IV administration of ANK-700/PBO through the D22 clinic visit.

The monitoring period is supported by nonclinical animal data, which demonstrate:

- ANK-700 is cleared from circulation in < 7 minutes, ensuring that > 5 half-lives have elapsed during the safety monitoring period
- T-cell tolerance induction can be observed as early as 1 week after drug administration in nonclinical models, ensuring the mechanism of action will be active and robust during the safety monitoring period
- Immunologically active antigen cannot be detected in animals 7 days after GP-peptide administration, ensuring that any processed antigen will be cleared during the safety monitoring period

AEs and any abnormal clinical parameters, including laboratory findings, observed during this period will be used by the SMC to determine whether dose escalation should proceed.

No patient with a DLT will be replaced.

In both parts, patients will be monitored in the clinic for 8 hours after the completion the first IV administration of ANK-700/PBO. In Part B, patients will be monitored in the clinic for 4 hours after completion of their second and third dose.

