### 5. STUDY POPULATION

### 5.1. INCLUSION CRITERIA

ANK-700

- 1. Male or female adults aged 18 to 60 years inclusive at screening
- 2. Diagnosed with RRMS per revised McDonald criteria (2017) with an EDSS score ≤ 6.5 at screening
- 3. Neurologically stable with no evidence of relapse within the 28 days prior to signing the informed consent form (ICF)
  - Note: Patients who experienced relapse during the screening period (i.e., after signing the ICF but before dosing) may be rescreened after 28 days
- 4. Either not currently receiving disease modifying MS therapy or currently using fumarate drugs (i.e. dimethyl fumarate, diroximel fumarate)
  - Note: Patients on fumarate drugs are only eligible if they have been on a stable dose  $\geq 6$  months before administration of study drug
- 5. Patients must use a highly effective method of birth control or are sterile or postmenopausal as confirmed by study Investigator for the first 3 months (through D90) of the study
- 6. Patient has signed and understands the ICF

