# **6.2.** SAFETY FOLLOW-UP VISIT

All patients in Part A will have a final Follow-Up Visit at D182 ( $\pm 7$  days), 6 months after the single administration of ANK-700.

All patients in Part B will have a final Follow-Up Visit at D365 ( $\pm 14$  days), approximately 1 year after the first administration of ANK-700.

Ongoing AEs considered at least possibly related to ANK-700 treatment should be followed until resolution, return to baseline, or are considered stable or chronic.

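### Section 11.2.8 ends pregnancy reporting at D15/D22 under the visit name that Section 6.2 gives to D182/D365, so up to 75 (Part A) or 68 (Part B) days of required contraception may carry no duty to report a new uncomplicated pregnancy

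*Protocol*

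**What the plan says.** **Pregnancy reporting.** Protocol Section 11.2.8 makes pregnancies in patients, and in partners of male patients, immediately reportable when they occur from study treatment "through the Safety Follow-Up Visit (D15 in Part A; D22 in Part B", followed by a reference to the patient's last dose. A covered pregnancy must reach the sponsor within 24 hours and be followed to its outcome, and normal births are to be notified too.

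**The same visit name elsewhere.** Section 6.2 is headed "SAFETY FOLLOW-UP VISIT". Its text reads "All patients in Part A will have a final Follow-Up Visit at D182" and "All patients in Part B will have a final Follow-Up Visit at D365".

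**What D15 and D22 are.** The list of abbreviations defines D as study day. In Section 4.7 the dose-escalation safety monitoring period runs "through the D15 clinic visit" in Part A and "through the D22 clinic visit" in Part B.

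**Contraception.** Inclusion criterion 5 (Section 5.1) requires it "for the first 3 months (through D90) of the study". Section 8 gives the same end date and says that the drug's effects on conception, pregnancy and lactation are not known.

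**Other routes.** SAE reporting (Section 11.2.6) runs to the final follow-up visit, and Section 11.2.8 sends SAEs during pregnancy and serious outcomes down that route. The SAP gives no pregnancy reporting window.

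**The concern.** One visit name carries two sets of dates, and the two give sites different instructions about when pregnancy reporting ends. A site that follows the bracketed days stops at about two weeks after the last dose. A site that looks up the named visit in Section 6.2 continues to D182 or D365.

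Under the first reading, the duty to report stops well before the duty to use contraception. A contraceptive failure after D15 or D22 that led to an uncomplicated pregnancy would not have to be notified, so its outcome need not be collected. The protocol's only scheduled pregnancy tests are at screening and before each dose (Sections 6.1.9 and 8), so the last is on D1 in Part A and D7 in Part B. After that the reporting clause is the main way the sponsor would learn of a pregnancy. This is a first-in-human study of a drug that Section 11.2.8 says has not been evaluated in pregnant or nursing women, so sites should not have to guess the end date.

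**Working it through.** The documents state no gap length, so there is no plan figure to reproduce. The check is a count of study days, using nominal visit days and ignoring visit windows.

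**Inputs**

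- Reporting cut-off in Section 11.2.8: D15 (Part A), D22 (Part B).
- Visit described in Section 6.2: D182 (Part A), D365 (Part B).
- End of required contraception (Sections 5.1 and 8): D90.
- Last dose (Section 4.3): D1 (Part A), D7 (Part B).

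**Days with contraception required but no duty to report, by reading**

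Gap = 90 − cut-off day, or 0 if the cut-off is at or after D90. The share is taken over D1 to D90.

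| Reading of the clause | Part A | Part B |
|---|---|---|
| D15/D22 as study days | 90 − 15 = 75 (D16 to D90); 75/90 = 83.3% | 90 − 22 = 68 (D23 to D90); 68/90 = 75.6% |
| 15 or 22 days counted from the last dose | cut-off 1 + 15 = D16; 90 − 16 = 74 | cut-off 7 + 22 = D29; 90 − 29 = 61 |
| Section 6.2 visit (D182/D365) | 0 | 0 |

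The first row follows the protocol's own definition of D. The second takes the clause's reference to the last dose literally. It shortens the gap by 1 day in Part A and 7 days in Part B but does not close it.

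**Effect of each possible correction, measured from D15/D22**

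| New end date | Days added, Part A | Days added, Part B |
|---|---|---|
| D90 | 75 | 68 |
| D182 / D365 | 182 − 15 = 167, of which 182 − 90 = 92 fall after D90 | 365 − 22 = 343, of which 365 − 90 = 275 fall after D90 |

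**Does another rule close the gap?**

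- *SAE reporting (11.2.6)* runs long enough, but an uncomplicated pregnancy meets none of the SAE criteria in Section 11.1.3.
- *AE recording (11.2.1)* also runs to the final visit. However, the AE definition in Section 11.1.1 does not name pregnancy, and an AE entry would not trigger the 24-hour notice or the outcome follow-up in Section 11.2.8.
- *Pregnancies that begin inside the window but are found later* remain reportable, because the clause turns on when the pregnancy occurs.

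The gap is therefore confined to pregnancies that are both new after D15/D22 and uncomplicated.

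**The case against.** The best defence is that the short window is deliberate. D15 is 14 days after the only Part A dose, and D22 is 15 days after the last Part B dose. Section 4.7 reports clearance from the circulation in under 7 minutes in nonclinical work and adds: "Immunologically active antigen cannot be detected in animals 7 days after GP-peptide administration". An exposure-based limit of about two weeks would be coherent, and a reporting window shorter than a precautionary contraception period is not in itself a contradiction. The protocol does not give this as its reason, though, and it sits awkwardly with contraception to D90 and with effects on pregnancy described as unknown. Even if the window is intended, the visit name is still wrong.

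Second, the naming conflict rests on the Section 6.2 heading alone. The body of that section, like Sections 6.1.15, 11.2.6 and 12.6, speaks of the final follow-up visit, and Section 11.2.8 prints its own days. That makes D15/D22 the more natural reading of the clause, which is the reading that produces the gap.

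Third, the clause says which pregnancies are immediately reportable. It does not say that later ones must not be reported. This stands as a caution: the gap is an absence of duty, inferred because no other section supplies a routine route. A site could still report voluntarily.

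Finally, no passage ties pregnancy reporting to the contraception period, so D90 is a reasoned choice and not one the text dictates.

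**Conclusion.** The inconsistency is real and the text needs correcting under either reading. If D15/D22 governs, a new uncomplicated pregnancy falls outside the reporting duty for 75 of 90 days in Part A and 68 of 90 in Part B while contraception is required. Counting from the last dose gives 74 and 61 days. If the Section 6.2 visit governs, there is no gap, and the bracketed days are the error.

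These are nominal calendar days, not expected missed reports; the documents give no pregnancy rate from which to estimate the latter. The severity is minor. The nonclinical clearance data make the safety risk low, serious outcomes are handled as SAEs, and sample size, the primary endpoint, the DLT rules and the descriptive analyses are untouched.

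**What to change.** In Section 11.2.8, replace the whole end-of-window clause (the visit name, the D15/D22 bracket and the reference to the last dose) with a single end date of D90 in both parts. That is the minimum that matches the contraception requirement, and it reduces the gap to zero.

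If the sponsor prefers to match the SAE window, name the final follow-up visit of Section 6.2 and print D182 (Part A) and D365 (Part B) beside it. The trade-off is that most of the added days (92 of 167 in Part A, 275 of 343 in Part B) fall after D90, when contraception is no longer required and Section 7.1 allows alternative disease-modifying therapies.

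In either case, D15/D22 should not be called the Safety Follow-Up Visit.

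The cost is one clause of protocol wording and at most a few more pregnancy reports in a study of about 33 to 42 patients. The SAP needs no change.
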